8.1 Screening Assessments

Eligible patients will have the following procedures performed within 3 weeks prior to study entry:

1. Medical history.
2. Physical examination including height (recorded only at baseline) and body weight.
3. Vital signs
4. Disease assessment (CT of chest, abdomen and pelvis for subjects with measurable disease; CT/MRI or Bone Scan for subjects with bone only disease, or PET/CT).
Bone scan to be performed on all patients at screening. PET/CT can be used in place if CT scan is diagnostic.
5. ECOG Performance Status
6. EKG with QTc measurement
7. Laboratory assessments including:
 - a. Clinical chemistry laboratory tests: Blood urea nitrogen (BUN), Creatinine, Calcium, Potassium, Sodium, Glucose, and
 - b. Hematology: Hematocrit (HCT), Hemoglobin (HGB), Platelet count, White blood cell count (WBC), and differential.
8. Liver Function Tests (LFT) including:
 - a. Alanine aminotransferase (ALT), Aspartate aminotransferase (AST), Alkaline Phosphatase, Total Bilirubin and Albumin.
9. Urinalysis with quantitative protein by dipstick. If > 100 by dipstick a UPC must be performed.
10. Thyroid function (TSH, free T3 and free T4).
11. Blood for circulating tumor cells.
 - a. One 7.5 ml CellSave tube, and one 10 ml purple top tube
12. Blood for cytokines
13. Archival tumor tissue collection: Paraffin-embedded tissue either at the time of diagnosis or disease relapse
14. Record all medication(s) received within 30 days prior to the first dose of study treatment and note if the medication is ongoing.

8.2 Pre-dose Assessments on Day 1

1. Physical examination (including body weight)
2. Vital signs (Subjects must have a pre-dose BP reading of $\leq 150/90\text{mmHg}$)
3. ECOG Performance Status
4. AE/SAE Assessments
5. Concomitant Medications

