1.2 Investigational Therapy

Pazopanib

Pazopanib is a potent, multi-targeted TKI of VEGFR-1, -2, -3, PDGFR- α and - β and c-kit, with IC₅₀ values of 10, 30, 47, 71, 84 and 74 nM, respectively[17]. It inhibits VEGF-induced VEGFR-2 phosphorylation in human umbilical vein endothelial cells (HUVEC) as well as in mouse lungs in a dose-dependent manner. Pazopanib shows significant growth inhibition of a variety of human tumor xenografts in mice, and also inhibits bFGF- and VEGF-induced angiogenesis in two mouse models of angiogenesis, the Matrigel™ plug assay and the cornea micropocket model.

To date, the safety experience includes over 1200 cancer subjects who have been treated in pazopanib studies. Over 850 subjects have received pazopanib monotherapy; the monotherapy safety profile described is based on 225 subjects with renal cell cancer treated with pazopanib. The most common AEs occurring in $\geq 10\%$ of subjects in decreasing order of frequency were diarrhea, fatigue, hair depigmentation, nausea, hypertension, dysgeusia, headache, anorexia, rash, vomiting, abdominal pain, cough, arthralgia, and constipation. Elevations in ALT of any Grade were reported in 50% of subjects with Grade 3 elevations in 6% and Grade 4 in < 1%. AST and ALT elevations occurred in parallel. Hyperbilirubinemia of any Grade occurred in 29% of subjects with Grade 3 elevations in 2%. No Grade 4 elevations have been reported. Concomitant elevations in transaminases and bilirubin have been observed in less than 1% subjects. Uncommon ($\leq 1\%$) but significant adverse events have been reported including: pulmonary embolism, venous thrombosis, hemorrhage, bowel perforation, myocardial infarction/angina, cerebrovascular accidents/TIA, atrial fibrillation, renal failure, and seizures.

Anemia, leukopenia, and thrombocytopenia were reported in 14 – 20% of subjects with Grade 3/4 abnormalities being uncommon ($\leq 2\%$). Hyponatremia of any grade was observed in 32% of subjects; with Grade 3 or 4 hyponatremia in 7% of subjects. Hyperkalemia of any grade was reported in 21% of subjects with Grade 3 or 4 hyperkalemia in 3% of subjects. Hyponatremia and hyperkalemia have not occurred concurrently in the same subject to suggest adrenal insufficiency. Increase in creatinine of any grade was reported in 25% with Grade 3 or 4 events in 1%. Elevations in amylase and lipase of any

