grade were reported in 16% and 17% respectively, with Grade 3 events in 1% and 5% respectively. Pancreatitis was reported in one subject. Increase in TSH was reported in 24% and a decrease in T4 in 18% of subjects.

Serial ACTH stimulation tests were conducted in two Phase I and two Phase II trials in cancer subjects. Adrenal insufficiency was not observed in 47 subjects for whom data was available. Twenty one of the 47 subjects had data beyond 24 weeks and 5 had data beyond 52 weeks. Additional pazopanib information is included in the pazopanib investigator brochure (IB).

In October, 2009, the U. S. Food and Drug Administration granted approval to pazopanib tablets (VOTRIENTTM, Novartis Pharmaceuticals) for the treatment of patients with advanced renal cell carcinoma.

The efficacy and safety of pazopanib were evaluated in an international, multicenter, randomized, double-blind trial comparing pazopanib to placebo in renal cell carcinoma who were treatment naïve or who had received prior cytokine therapy. All patients received best supportive care. The trial was conducted in patients with metastatic renal cell carcinoma stratified according to performance status, prior nephrectomy, and prior cytokine therapy.

A total of 435 patients were randomized (2:1) to receive pazopanib (n=290) or placebo (n=145). Demographics were balanced between the two arms. Progression-free survival (PFS) was the trial's primary endpoint. The median PFS was 9.2 and 4.2 months in the pazopanib and placebo arms, respectively (HR = 0.46, p value < 0.001). The effect was observed in both subgroups: treatment naïve (HR = 0.40) and cytokine pre-treated (HR = 0.54). After documented radiological progression, patients receiving placebo could receive pazopanib.

The overall survival results are not mature; 40% of patients had died by the time of data cut-off. The objective response rates were 30% and 3% for pazopanib and placebo, respectively. The median duration of responses was 13.5 months.

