Note for prior lapatinib: Subjects must have completed therapy with lapatinib at least 7 days prior to the first dose of study drug.

Note for prior trastuzumab: Subjects who received Q3 weekly, Q2 weekly or Q1 weekly must have completed therapy with trastuzumab at least 3 weeks, 2 weeks or 1 week, respectively, prior to the first dose of study drug.

9. Adequate hematologic and hepatic function as defined in Table 1.

Table 1 Definitions for Adequate Hematologic and Hepatic Function

System	Laboratory Values
Hematologic	
Absolute neutrophil count (ANC)	$\geq 1.0 \times 10^9/L$
Hemoglobin ^a	$\geq 9 \text{ g/dL} (5.6 \text{ mmol/L})$
Platelets	$\geq 100 \times 10^9/L$
Prothrombin time (PT) or international normalized ratio (INR) ^b	$\leq 1.2 \times \text{ULN}$
Activated partial thromboplastin time (aPTT)	$\leq 1.2 \times \text{ULN}$
Hepatic	
Total bilirubin	$\leq 1.5 \times \text{ULN}$ (except in patients with Gilbert's)
Alanine amino transferase (ALT) and Aspartate aminotransferase (AST) ^c	$\leq 2.5 \times \text{ULN}$
Renal	
Serum creatinine	$\leq 1.5 \text{ mg/dL} (133 \text{ } \mu\text{mol/L})$
Or, if $>1.5 \text{ mg/dL}$: Calculated creatinine clearance	$\geq 30 \text{ mL/min}$
Quantitative urine protein by dipstick	≤ 100
Urine Protein to Creatinine Ratio (UPC) ^d	≤ 1

- a. Subjects may not have had a transfusion within 7 days of screening assessment.
- b. Subjects receiving anticoagulant therapy are eligible if their INR is stable and within the recommended range for the desired level of anticoagulation.
- c. Concomitant elevations in AST/ALT above $1.0 \times \text{ULN}$ (upper limit of normal) are not permitted. Bilirubin ≤ 1.5 except if Gilbert's (elevation due to direct bilirubin)
- d. A UPC is required only if the urine protein is > 100 . If UPC > 1 , then a 24-hour urine protein must be assessed. Subjects must have a 24-hour urine protein value $< 1 \text{ g}$ to be eligible.

10. Subjects must have discontinued hormone replacement therapy (HRT) (e.g., conjugated estrogens tablets, USP or premarin), at least 28 days prior to receiving the first dose of randomized therapy.
11. Radiotherapy prior to initiation of therapy is allowed to a limited area (e.g., palliative treatment for painful bone metastases), if it is not the sole site of disease. Subjects must have completed treatment at least one week prior to starting study drugs, and must have recovered from all treatment-related toxicities.

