- ⁶ Blood urea nitrogen (BUN), Creatinine, Calcium, Potassium, Sodium, Glucose, Hematology: Hematocrit (HCT), Hemoglobin (HGB), Platelet count, White blood cell count (WBC), and differential are collected every 2 weeks until week 4, then every 4 weeks
- ⁷ Liver Function Tests (LFT) including Alanine aminotransferase (ALT), Aspartate aminotransferase (AST), Alkaline Phosphatase, Total Bilirubin and Albumin. Hematology: Hematocrit (HCT), Hemoglobin (HGB), Platelet count, White blood cell count (WBC), and differential. LFTs are collected every 2 weeks at weeks 3, 5, 7, and 9, then every 4 weeks and as clinically indicated.
- ⁸ UPC is required only if urine protein is $>$ 100.
- ⁹ CTCs will be collected at baseline, and then at 4 weeks, at 12 weeks and at the first visit documenting progression. One CellSave tube (7.5 ml) and one purple top tube (10 ml) should be sent at baseline, subsequent collections should include only one CellSave tube. Quantification of CTC will be conducted at [name] laboratory at UCSF
- ¹⁰ Serum will be collected at baseline and at 4 weeks. The cytokine levels will be measured by ELISA.
- ¹¹ Tissue biopsy is optional in this study, the safety of the biopsy will be determined by treating physicians.

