8.3.4 Every 4 weeks

1. Physical Exam including body weight
2. Vital Signs
3. ECOG Performance Status
4. Laboratory assessments including:
 - a. Clinical chemistry laboratory tests: Blood urea nitrogen (BUN), Creatinine, Calcium, Potassium, Sodium, Glucose, and
 - b. Hematology: Hematocrit (HCT), Hemoglobin (HGB), Platelet count, White blood cell count (WBC), and differential.
5. Liver Function Tests (LFT) including Alanine aminotransferase (ALT), Aspartate aminotransferase (AST), Alkaline Phosphatase, Total Bilirubin and Albumin.
6. Urinalysis with quantitative protein by dipstick. If > 100 by dipstick a UPC must be performed.
7. Adverse Event Assessment
8. Con Meds

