8.3.6 Every 16 weeks (after week 12)

1. Disease assessment (CT of chest, abdomen and pelvis for subjects with measurable disease [unless indicated sooner by clinical findings] or Bone Scan for subjects with bone only disease, or PET/CT). PET/CT can be used in place if CT scan is diagnostic.
2. 12-Lead EKG

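### Thyroid function is measured only at screening, although the protocol reports a TSH rise in 24% of pazopanib subjects; adding TSH to blood draws already planned would be a cheap improvement

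*Combined protocol and SAP*

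**What the plan says.** Section 8.1, item 10, lists "Thyroid function (TSH, free T3 and free T4") among the screening procedures. The matching row of the Schedule of Assessments has one mark, under Screening. The text and the table agree, so this is the intended schedule and not a slip between the two.

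The test does not appear in section 8.2 (Day 1), in 8.3.1 to 8.3.6 (treatment) or in 8.4 (follow-up). The four-weekly panel in 8.3.4 is "Clinical chemistry laboratory tests: Blood urea nitrogen (BUN), Creatinine, Calcium, Potassium, Sodium, Glucose", with hematology, liver tests and urinalysis alongside. Footnotes 6 and 7 of the Schedule, which define the laboratory and liver panels, do not mention thyroid tests. Tables 2 and 3 have no thyroid row.

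On eligibility, inclusion criterion 9 requires "Adequate hematologic and hepatic function as defined in Table 1". That table sets hematologic, hepatic and renal limits but no limit for TSH, T3 or T4. Section 3.3 has none either. Only exclusion 17, the general clause on serious or unstable conditions, could draw on the result.

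Section 1.2 gives the drug's record: "Increase in TSH was reported in 24% and a decrease in T4 in 18% of subjects". It introduces that account by saying that "the monotherapy safety profile described is based on 225 subjects with renal cell cancer treated with pazopanib".

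**The concern.** The protocol puts a figure on a laboratory effect of the drug, takes the baseline needed to detect it, and then plans no later value to compare with that baseline. The other safety laboratory rows of the Schedule (chemistry and hematology, liver tests, urinalysis, urine protein) are all repeated on treatment. Thyroid function is the only one that is not. Under section 5.2 treatment runs until progression, withdrawal of consent or unresolved toxicity, so some patients may take pazopanib for many months without a thyroid value.

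At stake is the detection of asymptomatic biochemical change in individual patients, and a descriptive count of such change under the secondary safety objective (section 2.2).

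**Working it through.** **1. Could any route other than the schedule lead to a test?**

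- Section 7.0 calls for the causes of adverse events to be investigated. This needs an adverse event first.
- The row of Table 2 for other clinically significant adverse events covers monitoring, interruption and reduction. It too starts from an event.
- Section 8.0 lets the investigator repeat a result outside the reference range. This needs an abnormal value first.

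None of these is triggered in a patient without symptoms whose screening result was normal. That is the whole extent of the gap.

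**2. How many thyroid changes might occur?**

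Inputs: TSH rise 24% and T4 fall 18% (section 1.2); n = 27 evaluable and 30 enrolled (section 12.6). Assumption: the rates carry over to this population and exposure. Half the rates are shown as a lower scenario. Expected count = n × p; the range is the central 95% of the binomial distribution.

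| Change | Rate | n = 27 | n = 30 |
|---|---|---|---|
| TSH rise | 24% | 27 × 0.24 = 6.5 (2–11) | 30 × 0.24 = 7.2 (3–12) |
| T4 fall | 18% | 27 × 0.18 = 4.9 (1–9) | 30 × 0.18 = 5.4 (2–10) |
| TSH rise, half rate | 12% | 27 × 0.12 = 3.2 (0–7) | 30 × 0.12 = 3.6 (1–7) |
| T4 fall, half rate | 9% | 27 × 0.09 = 2.4 (0–6) | 30 × 0.09 = 2.7 (0–6) |

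Chance of at least one TSH rise = 1 − (1 − p)^n:

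- at 24%: 1 − 0.76^27 = 0.9994 and 1 − 0.76^30 = 0.9997
- at 12%: 1 − 0.88^27 = 0.968 and 1 − 0.88^30 = 0.978

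These counts are changes of any degree. They are not counts of missed cases, because the documents do not give the share that is asymptomatic.

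**3. Would repeated testing estimate the rate well?**

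No. Seven of 30 is 23%, with an exact (Clopper-Pearson) 95% interval of 10% to 42%. If the 24% comes from the 225 renal-cancer subjects, it is 225 × 0.24 = 54 events, with an interval of 19% to 30%. The trial's own figure could not be told apart from the published one. The gain is detection in individual patients.

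**4. Do the proposed tests fit existing draws?**

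Footnote 6 of the Schedule says the blood tests it lists "are collected every 2 weeks until week 4, then every 4 weeks". Weeks 4, 8 and 12 are therefore draw dates. Section 8.3.6 is headed "Every 16 weeks (after week 12"), which gives weeks 12 + 16 = 28 and 28 + 16 = 44. Both are multiples of 4 and so fall on four-weekly draws. Section 8.4 already includes chemistry and hematology. No new visit or draw is needed.

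**The case against.** The case for leaving the schedule alone is that this is a monitoring preference. The safety endpoint in section 12.1 is adverse events and SAEs. Section 16.1.2 keeps laboratory abnormalities out of the adverse event record unless they are serious, need treatment or cause withdrawal. The documents give no grade or clinical consequence for the thyroid changes, and the rates appear to come from renal cancer. Exposure may be shorter here: section 1.2 gives a median PFS of 9.2 months on pazopanib in the renal cancer trial, against a median time to progression of 5.3 months in the breast cancer study. Thyroid is also not the only frequent effect left unscheduled. Amylase and lipase elevations of any "grade were reported in 16% and 17% respectively, with Grade 3 events in 1% and 5% respectively", and neither enzyme is measured at any visit.

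Most of this stands, and it is why the point is of low severity. It does not show that an asymptomatic change would be detected, and thyroid function is the effect for which the baseline is already paid for.

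Several stronger readings are tempting, and the documents do not support them:

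- A reader might infer that hypothyroidism in general would go unnoticed. Symptomatic cases can be worked up under section 7.0 and, if treated, serious or a cause of withdrawal, recorded as adverse events.
- A reader might infer that 6 or 7 patients would be missed. The number missed could be anywhere from none to all of those with a change.
- A reader might infer that the screening test is pointless. It could inform exclusion 17, and it is the comparator for any later symptom-driven test.
- A reader might infer that the safety endpoint is undermined, or that undetected thyroid change would distort dose reductions for fatigue. The endpoint as defined does not include untreated laboratory shifts, and the documents draw no link between thyroid change and fatigue.

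**Conclusion.** The point holds as a cheap improvement of low severity. Thyroid function is tested once, before treatment, with no specific eligibility limit attached, although the protocol itself reports frequent thyroid change on the drug. A site that follows the schedule exactly would not detect asymptomatic change in a patient with a normal baseline.

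If the quoted rates carry over, about 6 to 7 TSH rises and about 5 T4 falls of any degree would be expected in 27 to 30 patients, and roughly half as many at half the rates. How many would be asymptomatic is not given. The primary endpoint, the sample size and dosing are unaffected.

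**What to change.** 1. Add TSH, with free T4 if TSH is abnormal, at weeks 4 and 8 (section 8.3.4, marked as applying to those two weeks only), at week 12 (8.3.5), every 16 weeks thereafter (8.3.6) and at end of study (8.4). The limit in 8.3.4 matters: without it the test would be due every 4 weeks indefinitely and would be listed twice at weeks 12 and 28. The clinical team may prefer another interval.
2. Change the thyroid row of the Schedule of Assessments to match.
3. Tabulate post-baseline thyroid shifts separately from adverse events, because section 16.1.2 keeps untreated laboratory changes out of the adverse event record.

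Cost: at most 4 TSH assays per patient for weeks 4, 8, 12 and end of study, that is 27 × 4 = 108 to 30 × 4 = 120, plus one per 16 weeks for those continuing. If 20% to 50% of 30 patients continue (an assumption), that adds 6 to 15 assays at week 28. The text changes are one Schedule row, four lists and one safety table. They need a protocol amendment approved by the UCSF Protocol Review Committee and IRB and then by the Yale IRB, for which section 15.1 expects up to 90 days from receipt. An incidental abnormal TSH may also lead to further work-up.

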8.3 Assessments During Treatment Period

8.3.1. Every 2 weeks until week 4

1. Medical History
2. Physical Exam including weight
3. Vital Signs
4. ECOG Performance Status
5. Adverse Event Assessment
6. Con Meds

If stable without grade 2 or greater toxicity, visits can be decreased to monthly after the first 4 weeks of therapy.

8.3.2. Every 2 weeks (weeks 3, 5, 7, and 9) until week 9

1. Liver Function Tests (LFT) including Alanine aminotransferase (ALT), Aspartate aminotransferase (AST), Alkaline Phosphatase, Total Bilirubin and Albumin.

8.3.3. Week 4 only

1. 12-Lead EKG
2. Blood for CTC. One CellSave tube (7.5 ml) will be drawn.
3. Blood for cytokines

8.3.4 Every 4 weeks

1. Physical Exam including body weight
2. Vital Signs
3. ECOG Performance Status
4. Laboratory assessments including:
 - a. Clinical chemistry laboratory tests: Blood urea nitrogen (BUN), Creatinine, Calcium, Potassium, Sodium, Glucose, and
 - b. Hematology: Hematocrit (HCT), Hemoglobin (HGB), Platelet count, White blood cell count (WBC), and differential.
5. Liver Function Tests (LFT) including Alanine aminotransferase (ALT), Aspartate aminotransferase (AST), Alkaline Phosphatase, Total Bilirubin and Albumin.
6. Urinalysis with quantitative protein by dipstick. If > 100 by dipstick a UPC must be performed.
7. Adverse Event Assessment
8. Con Meds

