The most common adverse reactions (greater than or equal to 20%) were diarrhea, hypertension, hair color changes, nausea, anorexia, and vomiting. Grade 3/4 adverse reactions that differed by greater than or equal to 2% between arms were abnormal hepatic function, diarrhea, hypertension, and proteinuria. QT prolongation has been seen with pazopanib. Laboratory abnormalities occurring in >10% of patients and more commonly (>5%) in the pazopanib arm included increased transaminases, hyperglycemia, leukopenia, hyperbilirubinemia, neutropenia, hypophosphatemia, thrombocytopenia, lymphocytopenia, hyponatremia, hypomagnesemia, and hypoglycemia. Deaths due to serious adverse events include cerebrovascular accident, gastric cancer, gastrointestinal hemorrhage, hemoptysis, bowel perforation, cardiac failure, myocardial infarction, hepatic failure and pneumonia occurred more commonly in the pazopanib arm. Hepatic dysfunction is included as a boxed warning in the product label and two deaths were associated with hepatic failure.

Recently, a phase II trial was designed for patients with metastatic breast cancer, who failed 2-3 prior chemotherapy. Total 20 patients were recruited in this study, 70% were ER+, and all were Her-2/neu negative. Pazopanib monotherapy was given at 800 mg daily. One patient (5%) had a partial response, 11 (55%) had stable disease (SD) [four (20%) with SD > or = 6 months], and seven (35%) had progressive disease as their best response. One (5%) was not evaluable. The median time to progression was 5.3 months. Pazopanib did not cause significant severe toxicity aside from grade 3-4 transaminitis, hypertension, and neutropenia in three patients each (14% each) and grade 3 gastrointestinal hemorrhage in one patient (5%)[18].

Standard therapy for hormone receptor positive metastatic disease.

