7.0 Toxicity Management & Dose Modifications

At each visit during the Treatment Period, subjects should first be evaluated for the occurrence of AEs and laboratory abnormalities. The potential causes of the adverse events should be thoroughly investigated and confounding factors should be identified and eliminated whenever possible.

Treatment emergent hypertension or proteinuria is relatively common in subjects receiving pazopanib and is handled by dose modification of pazopanib. Some adverse events, although rare, can result in significant clinical consequence such as arterial/venial thrombosis, severe hemorrhage, bowel perforation and severe fatigue/asthenia, therefore should be promptly identified and managed. Some clinical signs and symptoms may be early indicators for severe toxicity that should be thoroughly investigated (e.g., abdominal pain may be an early sign for bowel perforation).

Specific recommendations for management of these possible AEs along with guidelines for dose delay/modification or discontinuation of study treatment are provided in Tables 2 and 3.

If dose reduction of pazopanib is necessary, the dose should be reduced stepwise by 200 mg at each step, and the subject should be monitored for 10 to 14 days at each dose level. If toxicity does not abate during this monitoring time, pazopanib may need to be interrupted and/or the dose further decreased with continued monitoring for an additional 10-14 days at each dose level, and so on.

If the toxicity has abated with reduction of the dose and dose re-escalation is considered safe by the investigator, the dose can then be increased step-wise back to the pre-event dose (in 200 mg increments, after monitoring for 10-14 days at each dose level to ensure that toxicity did not recur or worsen).

If a subject's treatment has been interrupted for more than 21 days, the Investigator must contact the PI to review the subject's condition in order to resume the treatment.

Dose Interruptions/Modifications for Specific, Non-liver Related, Toxicities

Recommendations for investigational product dose interruptions/modifications in case of specific treatment-emergent AEs are provided in Table 2.

Table 2 Dose Modification Algorithms for Potential Treatment-Related Adverse Events

AE Terms & Descriptions	Dose Modification Algorithms
Hypertension^a	

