Grade 3 or 4, or Recurrent \geq Grade 2 event after dose interruption/reduction.

Discontinue pazopanib and continue with follow-up per protocol.

Venous Thrombosis (DVT, PE)

Grade 1 and 2

Continue pazopanib with same dose; initiate and monitor anticoagulation as clinically indicated.

Grade 3 or >

Discontinue pazopanib and continue follow-up per protocol.

Grade 4 and/or PE

Discontinue pazopanib and continue follow-up per protocol.

Arterial Thrombosis/Ischemia

Any Grade

Discontinue pazopanib and continue follow-up per protocol.

Thrombocytopenia: Investigate and document underlying cause

Grade 1 or 2

Continue pazopanib with current dose; monitor as clinically indicated.

Grade 3 or 4

Step 1. Interrupt pazopanib until toxicity resolves to \leq Grade 2.
Step 2. Restart pazopanib dose-reduced by 200 mg and monitor as clinically indicated.

If no recovery to \leq Grade 2 or recurrent Grade 3 or 4 thrombocytopenia, discontinue pazopanib and follow-up per protocol

Anemia: No specific dose reduction rules are indicated for anemia unless due to hemorrhage or bleeding as noted above.

Palmar-plantar Erythrodysesthesia Syndrome

Grade 1	1. Continue IP at present dose
Minimal skin changes or dermatitis without pain (erythema, oedema, hyperkeratosis)	
Grade 2	1. Hold IP 2. Treat as clinically appropriate 3. Upon resolution to Level 1 or better restart IP with a dose reduction to 400 mg 4. If recurrent consider a further dose reduction to 200mg or discontinuation
Skin changes with pain; limiting instrumental activities of daily living (ADLs) (peeling, blisters, oedema, bleed, hyperkeratosis)	
Grade 3	1. Discontinue IP
Severe skin changes with pain and limiting self care	

Other Clinically Significant Adverse Events ^c

Grade 1	Continue pazopanib; monitor as clinically indicated.
Grade 2 or 3, if clinically significant	Step 1. Interrupt pazopanib until toxicity resolves to \leq Grade 1. Step 2. Restart pazopanib dose-reduced by 200 mg and monitor as clinically indicated.
Grade 4	Discontinue pazopanib and continue follow-up per protocol.

Prolongation of QTc Interval: If the QTc is prolonged, the ECG should be manually read to ensure accuracy of the reading. The values below refer to manually-read ECGs.

QTc \geq 480 < 500 msec	Continue pazopanib; monitor as clinically indicated.
QTc \geq 500 msec	Discontinue pazopanib and continue follow-up per protocol.
a.	Patients are encouraged to self-monitor BP twice a week

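### Low magnesium and low phosphate, two of the 11 laboratory abnormalities that Section 1.2 lists as more common on pazopanib, have no baseline or scheduled test

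*Combined protocol and SAP*

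**What the plan says.** In its account of the randomized renal-cancer trial, Section 1.2 states: "Laboratory abnormalities occurring in >10% of patients and more commonly (>5%) in the pazopanib arm included" a list of 11 items. The first five are raised transaminases, high glucose, low white cells, raised bilirubin and low neutrophils. The other six are "hypophosphatemia, thrombocytopenia, lymphocytopenia, hyponatremia, hypomagnesemia, and hypoglycemia".

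The chemistry panel is "Clinical chemistry laboratory tests: Blood urea nitrogen (BUN), Creatinine, Calcium, Potassium, Sodium, Glucose". The same six analytes appear in Section 8.1 (item 7a, screening), Section 8.3.4 (item 4a, every 4 weeks), Section 8.4 (item 6a, follow-up) and footnote 6 to the Schedule of Assessments. Footnote 6 says the samples "are collected every 2 weeks until week 4, then every 4 weeks". Hematology with differential is scheduled alongside, and a liver panel is scheduled at screening and on treatment.

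Section 16.1.2 keeps a laboratory abnormality out of the adverse event record unless it is serious, needs treatment or leads to withdrawal. Section 12.1 defines the safety endpoint as adverse events and SAEs.

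**The concern.** The protocol names these two abnormalities as more frequent on the study drug, monitors the other nine on the same list, and gives no reason for leaving these two out. Without a scheduled test, a low value that causes no symptoms is unlikely to be seen. If one is found later, there is no pre-treatment value to show whether it is new.

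This is a patient-safety point. A low magnesium or phosphate that needs treatment counts as an adverse event under Section 16.1.2, but nobody can judge that it needs treatment until it has been measured. The effect on the reported safety endpoint is small, because most untreated values would be left out of it even if they were measured.

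**Working it through.** The plan gives no figure of its own on this point, so the main check is to match the list against the scheduled tests.

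**Coverage of the Section 1.2 list at screening (8.1) and every 4 weeks (8.3.4)**

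| Listed abnormality | Scheduled test |
|---|---|
| Raised transaminases | ALT, AST |
| Raised bilirubin | Total bilirubin |
| High glucose | Glucose |
| Low glucose | Glucose |
| Low sodium | Sodium |
| Low white cells | WBC |
| Low neutrophils | Differential |
| Low lymphocytes | Differential |
| Low platelets | Platelet count |
| Low magnesium | None |
| Low phosphate | None |

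That is 9 of 11 covered and 2 not covered. Neither analyte appears in the eligibility laboratory table (Table 1), in the dose-modification tables (Tables 2 and 3) or in the Section 8.4 panel. Their only mention is in the Section 1.2 list.

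**Possible number of cases**

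Inputs: n = 27 evaluable patients (Section 12.6). Section 1.2 gives a threshold of more than 10% for joining the list, not a rate for either analyte, and that sentence gives no grade. Using 10% here is therefore an assumption; 5% and 20% show the range. The expected count is n × p, and the chance of at least one case is 1 − (1 − p)^n, for each abnormality separately.

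| Assumed p | Expected cases | Chance of at least one |
|---|---|---|
| 5% | 27 × 0.05 = 1.35 | 1 − 0.95^27 = 75% |
| 10% | 27 × 0.10 = 2.7 | 1 − 0.90^27 = 94% |
| 20% | 27 × 0.20 = 5.4 | 1 − 0.80^27 = 99.8% |

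At 10%, the 95% binomial range for the count is 0 to 6. Not all of these cases would be due to the drug. If the 5% in Section 1.2 is read as the minimum absolute difference between arms, the excess at the threshold is 27 × 0.05 = 1.35 of the 2.7 cases, and a single-arm trial cannot tell which ones.

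Testing would serve detection and would not give a precise rate: 3 cases in 27 has an exact 95% confidence interval of 2.4% to 29%.

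**Added assays through week 12, two analytes, 30 enrolled patients**

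- Screening and weeks 4, 8 and 12: 30 × 4 × 2 = 240.
- With the week 2 sample in footnote 6: 30 × 5 × 2 = 300.

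Both figures assume that every patient stays on treatment to week 12, so they are upper figures.

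**The case against.** The strongest case against is that panel content is a design preference with little consequence here. The panels are introduced with the word *including*, so a site may add tests. Section 7.0 says "The potential causes of the adverse events should be thoroughly investigated". Section 16.1.2 excludes most untreated values from adverse events, and Section 16.2.1 describes database entry for Grade 3 and above. The incidence comes from a renal-cancer trial, and no severity is given for either analyte.

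Much of this stands, and it limits the size of the point. It does not remove it. *Including* permits these tests but does not require them, so detection would depend on local habit at two sites. Cause-finding begins once an adverse event has been noticed, and an asymptomatic low value gives no such prompt.

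Three stronger readings are tempting, and the documents do not support them.

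- **A QT hazard from unmeasured magnesium.** Section 1.2 says "QT prolongation has been seen with pazopanib", EKGs fall to every 16 weeks after week 12, and the QTc row of Table 2 names no electrolyte check. A reader might infer that low magnesium adds to the QT risk and should come first. The documents nowhere link magnesium to QT. They also contain direct QT safeguards: exclusion above 480 msec, EKGs at screening, week 4 and week 12, discontinuation at 500 msec or more, and a ban on listed drugs, some of them named for QT risk.
- **Electrolyte loss through diarrhea.** Appendix III mentions electrolyte imbalance, but its flow chart is not shown in the text available and may itself call for electrolyte tests. It cannot be counted against the plan.
- **Monitoring that is complete apart from these two.** Section 1.2 also reports raised amylase (16%), raised lipase (17%, Grade 3 in 5%), raised TSH (24%) and decreased T4 (18%). Amylase and lipase are in no panel, and thyroid function is tested at screening only.

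**Conclusion.** The point holds as a minor, inexpensive safety improvement. Of the 11 abnormalities in the Section 1.2 list, low magnesium and low phosphate alone have neither a baseline nor a scheduled test, and asymptomatic cases would be found only by chance. That part rests on the documents directly.

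The size is uncertain. About 2.7 of 27 patients with each abnormality depends on a 10% rate carrying over from renal cancer to breast cancer, with grade unknown and only part of it attributable to pazopanib. The documents give no basis for ranking one analyte above the other. The 12-week clinical benefit endpoint and the two-stage rule are unaffected.

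**What to change.** Add magnesium and phosphate to the chemistry panel in Sections 8.1, 8.3.4 and 8.4 and in footnote 6, run on the samples already scheduled. Summarise the CTCAE v4.0 laboratory grades for the two analytes, including change from baseline, in a table separate from adverse events, since Section 16.1.2 would otherwise leave most of the values unreported. Action on an individual result is a matter for the clinical leads. The sponsor may wish to decide on amylase, lipase and on-treatment thyroid tests at the same time, but this change does not depend on that.

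The cost is 240 to 300 assays through week 12, then two per patient every 4 weeks and two at end of study. No extra visit is needed. That no extra tube is needed is an assumption, because the documents give neither tube volumes for chemistry nor assay prices. New data fields are needed at two sites, and some asymptomatic results will need clinical review.
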